2.4 RANDOMIZATION (OR STRATIFICATION) PROCEDURES

After confirmation of eligibility at Central Registration Office, CRO staff will provide the research team with the randomized treatment assignment. Patients will be randomized to receive TT alone or TT+ pCND. Randomization will be conducted a 1:1 fashion using variable block sizes. Written confirmation of registration to the protocol and the randomization arm selected will be obtained from the CRO and placed on the patient's research record.

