3 STUDY IMPLEMENTATION

3.1 STUDY DESIGN

This is a prospective, randomized, single-blinded, controlled trial in patients with a suspicious or confirmed PTC ≤ 4 cm without clinical evidence of lymphadenopathy or extrathyroidal extension on imaging. Preoperative evaluation will be performed to establish the baseline status of participant's QOL, neck pain (scale 1 to 10), subjective voice and objective vocal cord function, and swallowing status using standardized questionnaires (see below). *BRAF* V600E mutation status of the tumor will be assessed in all patients after thyroidectomy. Enrolled participants will be randomly assigned preoperatively to receive either TT alone or TT with pCND. Participants and their families will be blinded from the results of randomization. If a patient who is assigned to TT alone group is found to have LNM intraoperatively by frozen section, a CND will be performed and the patient will remain in TT alone group (intention to treat). Participants in both groups will receive uniform, routine postoperative care and follow-up evaluation per protocol (see below). Stim-Tg will be measured in all participants prior to remnant ablation at 3 months postoperatively (prior to remnant ablation, if indicated). Stim-Tg at 1-year post-remnant ablation or 1 year postoperatively if participants do not receive remnant ablation will be performed in patients enrolled at the NIH but is optional in patients enrolled at non-NIH site(s). Tg and anti-thyroglobulin antibodies will be measured annually for 10 years. The postoperative complications and QOL of participants will be assessed during preoperative evaluation, postoperative day 1, 2 weeks, 3 and 6 months, 1, 5 and 10 years postoperatively. Surgical outcome will be evaluated at postoperative day 1, 2 weeks, and 6 months postoperatively. Participants will have an evaluation for radioactive iodine ablation by the

Abbreviated Title: Prophylactic Central Neck Dissection

Version Date: 01/15/2019

endocrinology service. The standardized protocol will be used based on histologic findings and patient's risk of recurrence per NIDDK protocol. (**Table 2**) Similarly, participants will be managed using a standardized protocol for TSH suppression therapy based on the risk of recurrence.

Table 2. Post-operative risk stratification: Guideline for management of patients with clinical characteristics that modify initial assessment of risk¹

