6 SAFETY REPORTING REQUIREMENTS/DATA AND SAFETY MONITORING PLAN

No experimental treatments or procedures are performed as a part of this protocol and therefore no adverse events are expected. In the unlikely event that an adverse event occurs that is attributable to the research, CTCAE v. 4.0 will be used for grading such events. Patients who meet the standard of care criteria for resection of their disease will undergo a major operative procedure and may receive extensive care in the ICU. The principal investigator or designee will closely monitor and document the clinical care and treatment of each patient as per standard of care at the NIH Clinical Center. As per NIH Clinical Center standards of practice, the Occurrence Reporting System will be used to report any clinical events meeting these reporting criteria.

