6.2.2 NIH Intramural IRB Requirements for PI Reporting at Continuing Review

The protocol PI will report to the NIH Intramural IRB:

1. A summary of all protocol deviations in a tabular format to include the date the deviation occurred, a brief description of the deviation and any corrective action.
2. A summary of any instances of non-compliance
3. A tabular summary of the following adverse events:
 - All Grade 2 **unexpected** events that are possibly, probably or definitely related to the research;
 - All Grade 3 and 4 events that are possibly, probably or definitely related to the research;
 - All Grade 5 events regardless of attribution;
 - All Serious Events regardless of attribution.

NOTE: Grade 1 events are not required to be reported.

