6.3 NCI GUIDANCE FOR REPORTING EXPEDITED ADVERSE EVENTS FOR MULTI-CENTER TRIALS

The site PI must immediately report to the coordinating center PI any serious adverse event, whether or not considered treatment related, including those listed in the protocol and must include an assessment of whether there is a reasonable possibility that the treatment caused the event within 24 hours of PI awareness of the event. The site PI will use CCR Problem report form ([Appendix I](#)). The Site PI must also report any protocol deviations to the coordinating center PI within 7 days of PI awareness. Participating centers must also submit the report to their IRB in accordance with their institutional policies.

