Beginning in the first spring after twenty total patients have been randomized and treated on the trial, the study will be monitored by the DSMB on an annual basis to evaluate the safety of the two arms. The SAEs (typically grade 3 toxicities, or greater) will be reported according to type of toxicity, and maximal grade noted per patient, for toxicities with at least a possible attribution to the therapy provided on that arm. Comparisons will be made between the two arms using a Cochran-Armitage test for trend, or other appropriate methods, to determine if there is increased toxicity associated with either arm.

In addition, at the first DSMB meeting held following the point at which half of the required total subjects have been enrolled and evaluated, an interim evaluation for greater than expected difference in fractions with athyroglobulinemia will be performed. Specifically, after 90 total patients who do not have anti-thyroglobulin antibody have been evaluated, using an O'Brien-Fleming approach, if the two-tailed p-value for a comparison of the two rates is <0.0054 , then the trial will be stopped at that time and a significant difference declared. While invoking this boundary at an interim point will technically require that the final p-value be 0.0492 or less for the overall significance level to be retained at a 0.05 level, as a practical matter, $p<0.05$ will still be required to declare a significant result.

In addition, a single interim evaluation for futility will also take place after 90 evaluable patients accrued. At the same DSMB meeting as the single interim evaluation for efficacy, the study will be evaluated for futility as follows: if the fraction with athyroglobulinemia on the arm with TT + pCND is identical to or lower than that of the TT alone arm, then accrual will stop because of very small probability of achieving a statistically significant difference in favor of the combination arm if the trial were to be completed.

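### The DSMB's safety comparison of the arms counts only events attributed to that arm's therapy, with no blinded assessor named; an all-SAE table should come first

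*Combined protocol and SAP*

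**What the plan says.** Section 7 provides for annual DSMB review of the safety of the two arms, beginning in the first spring after twenty patients have been randomised and treated. On content it says: "The SAEs (typically grade 3 toxicities, or greater) will be reported according to type of toxicity, and maximal grade noted per patient", and it limits this to events "for toxicities with at least a possible attribution to the therapy provided on that arm". It continues: "Comparisons will be made between the two arms using a Cochran-Armitage test for trend, or other appropriate methods". It gives no significance level, safety boundary or assessor of attribution.

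On who knows the arm:

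- Section 3.1: "Participants and their families will be blinded from the results of randomization".
- Section 2.4: "CRO staff will provide the research team with the randomized treatment assignment".
- Section 6.3: the site principal investigator's SAE report "must include an assessment of whether there is a reasonable possibility that the treatment caused the event".
- Section 6.4.1: the principal investigator reviews each patient's adverse event data.

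Reporting without an attribution filter exists, but goes elsewhere. At continuing review the IRB receives "All Serious Events regardless of attribution" (Section 6.2.2), and under Section 6.3 participating sites send every SAE to the coordinating centre, related or not.

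**The concern.** Patients with an event in each arm can be compared fairly because allocation was random. A causality judgement made after surgery, by someone who may know the operation performed, inserts a non-random step between the event and the count. If the judgement runs differently in the two arms, the counted rates differ for reasons other than harm: a real excess with pCND can shrink, or an apparent excess can arise from equal true rates.

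Two features leave room for this. The reference therapy is total thyroidectomy in one arm and thyroidectomy plus pCND in the other. Also, a patient in the TT-alone arm with a positive frozen section receives a therapeutic dissection and stays in that arm (Section 3.1), and the plan does not say whether a complication of that dissection counts as attributable to that arm's therapy.

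Section 9.5 names complications of pCND as the main risk of taking part, so this is the comparison the DSMB most needs to be able to read.

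**Working it through.** **Text check.** Section 7 contains one planned between-arm comparison of serious harm, and it is filtered. No all-cause comparison for the DSMB appears in Section 6 or Section 7. Hypoparathyroidism, vocal cord dysfunction and wound complications are secondary outcomes without a filter (Section 1.1.2), but among secondary outcomes Section 7 describes an arm comparison only for quality of life, swallowing and pain. That the assessors know the arm is an inference: Section 7 names nobody, but Sections 2.4, 3.1, 6.3 and 6.4.1 together describe no blinded alternative.

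**Illustration.** The plan states no power or error rate for the safety comparison, so there is no figure to reproduce.

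Inputs:

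- Patients per arm: the accrual ceiling of 225 with 1:1 allocation (Sections 7 and 2.4) gives 225 / 2 = 112.5, taken as 112.
- True event rates and attribution shares: assumptions, because the documents give none by arm.
- Test: pooled two-proportion z-test, two-sided 0.05, on patients with any counted event, standing in for the trend test.

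Formulas:

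- Counted rate = true rate × share of events attributed.
- z = |p1 − p2| / √[p(1 − p) × 2/n], where p1 and p2 are the observed counted proportions, p is their mean and n = 112; reject if z > 1.96.
- Rejection probability = the sum of the binomial probabilities of all pairs of counts that reject.

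| True rate, TT / TT+pCND | Share attributed | Counted rate | Probability of p < 0.05 |
|---|---|---|---|
| 10% / 10% | all / all | 10% / 10% | 5.3% |
| 10% / 10% | 85% / 95% | 8.5% / 9.5% | 6.1% |
| 10% / 10% | 70% / 90% | 7% / 9% | 8.9% |
| 10% / 10% | 50% / 90% | 5% / 9% | 22.0% |
| 5% / 15% | all / all | 5% / 15% | 73.5% |
| 5% / 15% | 70% / 70% | 3.5% / 10.5% | 56.1% |
| 5% / 15% | 90% / 50% | 4.5% / 7.5% | 15.4% |

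The first four rows show a difference being created, the last three a difference being hidden. With 70% attributed in both arms the ratio of rates is still 3 (10.5 / 3.5), so equal attribution costs power but does not distort the relative contrast.

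**Sensitivity.**

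- Fisher's exact test gives lower figures and the same pattern: 2.8% rising to 14.9% for the 50% v 90% split, and 63.7% falling to 9.9% for the 90% v 50% split. With 90% attributed in both arms, power falls only from 63.7% to 58.0%.
- Section 9.5 puts major complications of adding pCND below 1%. At a true rate of 1% in both arms, about 1.1 patients per arm (112 × 0.01), the z-test rejects about 1–2% of the time with or without the 50% v 90% filter. Testing says little there, and what matters is which individual events the DSMB sees.
- Early reviews have fewer patients. At 30 per arm, unfiltered power for 5% v 15% is only 26%.

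**The case against.** The strongest reply is that the threshold is low. A merely possible link is enough, both arms undergo total thyroidectomy, and Section 9.4 lists bleeding, infection, nerve injury, voice and swallowing problems and hypocalcaemia as risks of thyroidectomy with or without pCND. Most perioperative complications would be counted in either arm. This stands: it makes a 50% v 90% split extreme and confines the likely effect to late, non-specific or medical events.

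Three stronger readings are tempting and not supported.

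- A reader might infer that the filter removes the randomised contrast. It does not: with equal attribution the contrast remains and only power is lost.
- A reader might take the statement in Section 6, "No experimental treatments or procedures are performed as a part of this protocol and therefore no adverse events are expected", as telling investigators not to attribute events. In context it concerns harm from the research, with surgery treated as standard of care; the same section goes on to describe a major operation and its monitoring, and Sections 9.4 and 9.5 list surgical harms. It is loosely worded, but it sets no rule for attribution to therapy under Section 7, and any effect on attribution is conjecture.
- A reader might infer that the filtered comparison is the only protection against excess harm. Unfiltered serious events reach the IRB and the coordinating centre, and the main complications are secondary outcomes. None of these, however, is an arm comparison planned for the DSMB.

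**Conclusion.** The point holds as a weakness in the rule, not as a demonstrated bias. The DSMB comparison depends on a causality judgement for which no blinded assessor is named, and it can be biased in either direction if that judgement differs by arm. The size cannot be determined from the documents. Under the assumed 10% rates and 112 per arm it runs from negligible (6% false signals against 5%, for 85% v 95%) to substantial (22%, for 50% v 90%). The rates of 10% to 15% used above exceed the figure of under 1% for major complications in Section 9.5, although that figure need not cover every SAE. This is a cheap improvement worth making; it gives no reason to think the monitoring already done is wrong.

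**What to change.** In Section 7, make the DSMB's primary safety table and arm comparison all SAEs, including all deaths, by randomised arm in all randomised and operated patients, regardless of attribution. Keep events attributed to therapy as a secondary table, and state who makes the attribution and whether that person knows the arm.

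For SAEs this needs one extra table and no new data collection, because Sections 6.2.2 and 6.3 already require serious events to be reported regardless of attribution. The same cannot be assumed for non-serious grade 3–4 events: Section 6.2.2 tabulates grade 3 and 4 events only when at least possibly related to the research. Include those regardless of attribution only where they are already recorded. The downside is that some unrelated events will add noise to the primary table; the secondary table lets the DSMB see how much.

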1. INTRODUCTION

1.1 STUDY OBJECTIVES

1.1.1 Primary Objective:

- To determine biochemical cure rates in patients with low-risk PTCs undergoing total thyroidectomy (TT) with and without pCND as measured by postoperative TSH-stimulated serum thyroglobulin (stim-Tg) at 3 months (prior to RAI treatment).

1.1.2 Secondary Objectives:

- To determine biochemical cure rates in patients with low-risk PTCs undergoing total thyroidectomy (TT) with and without pCND as measured by postoperative TSH-stimulated serum thyroglobulin (stim-Tg) at 1 year postoperatively in patients who will not receive RAI or 1 year post remnant ablation.
- To determine the following outcome measures in patients undergoing TT with and without pCND:
 - a. The QOL of patients with low-risk PTCs undergoing TT and pCND to those undergoing TT alone using the SF-36v2 standardized questionnaire (preoperative, postoperative day 1, 2 weeks, 3 and 6 months, 1, 5 and 10 years postoperatively).
 - b. Neck pain (preoperative, postoperative day 1, 2 weeks, and 6 months postoperatively).
 - c. Subjective voice quality, swallowing impairment (preoperative, postoperative day 1, 2 weeks, and 6 months postoperatively) as well as objective vocal cord dysfunction (preoperative and postoperative day 1 and 6 months postoperatively only if abnormality is found on postoperative day 1) and requirement for intervention.
 - d. Rate and duration of both symptomatic and asymptomatic hypoparathyroidism including requirement and duration of postoperative oral or IV calcium replacement as well as vitamin D analogue for hypoparathyroidism (preoperative PTH, postoperative day 1, 2 weeks and 6 months postoperatively).
 - e. Rate of cervical wound complications (hematoma, seroma, and surgical site infection) and intervention(s) required.
 - f. The use of radioactive iodine.
 - g. Oncologic outcome:
 - I. Radiographic evidence with biopsy or pathology proven recurrent disease.
 - II. Thyroid cancer-related death.
 - h. The impact of BRAF V600E mutation status on lymph node metastasis in patients with low-risk PTC undergoing TT with or without pCND. In addition, we will compare the rate of disease recurrence in patients undergoing pCND to those who will not undergo pCND, by BRAF V600E mutation status.

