To assess the completeness of surgery, some studies have compared the postoperative stim-Tg level between those who underwent pCND and those who did not with conflicting results (34, 44-46). Hughes et al. retrospectively compared stim-Tg levels at pre and 1-year post remnant ablation in 143 patients with clinical node-negative PTC who underwent TT with and without pCND and found no significant difference(34). Retrospective studies from Hong Kong showed a significant lower stim-Tg before remnant ablation and higher rate of patients with undetectable thyroglobulin in TT and pCND group but no difference was observed at 6 months post remnant ablation(44). Another study reported that post-ablative stim-Tg was inversely correlated with the number of lymph nodes removed from pCND, suggesting pCND resulted in more complete eradication of (microscopic) tumor foci (45). A large retrospective study (n=447) by Sywak et al. demonstrated a significantly lower post-ablative stim-Tg and higher rates of athyroglobulinemia in patients who had TT with pCND(46). These discordant results highlight the need for randomized trial that is free of selection bias and all participants undergo the same treatment

Abbreviated Title: Prophylactic Central Neck Dissection

Version Date: 01/15/2019

protocol. A summary of the controversial results surrounding the effects of pCND is demonstrated in **Table 1**.

Table 1. A summary of the controversial effects of pCND¹ on the various clinical parameters in patients with PTC.

Outcome measures	Study authors	Type of study	Sample size (n)	Results	Remarks
Biochemical cure rate measured by stim-Tg ²	Hughes et al. (34)	Retrospective	143	No difference in stim-Tg before or 1 year post-RAI ⁽³⁾	
	Sywak et al. (46)	Retrospective	447	Lower post-RAI stim-Tg and higher rate of athyroglobulinemia	
Locoregional recurrence	Lang et al. (39)	Meta-analysis	3,331	35% reduction in risk of locoregional recurrence	Data from retrospective studies, confounded by selection bias and the use of RAI
	Wada et al. (47)	Retrospective	390	No difference	
The use of RAI	Vaisman et al. (48)	Prospective	104	Decrease use of RAI due to higher rate of athyroglobulinemia	
	Hughes et al. (34)	Retrospective	143	Increase RAI dosage due to upstaging	

Abbreviated Title: Prophylactic Central Neck Dissection

Version Date: 01/15/2019

Postoperative complications	Giordano et al. (35)	Retrospective	1,087	Increase rate of transient and permanent hypoparathyroidism	

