3.3.2 Recurrent Disease

Surveillance for persistent or recurrence disease will be performed every year for 10 years. The study blind will be broken after the 10 year visit unless medically necessary for the patient's continued care. Work up includes:

- a. Detailed history and physical examination in clinic.
- b. Calcium total, Ionized Calcium, Magnesium total (Mg), Inorganic Phosphorus, TSH, Tg (while on levothyroxine), anti-thyroglobulin antibodies.
- c. Soft tissue neck USG.
- d. Other radiographic imaging or nuclear scintigraphy as clinically indicated.
- e. QOL using SF-36 v2 questionnaire will be assessed at 5 and 10 years postoperatively.

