3.3.3 Off Study Criteria

- Absence of thyroid cancer in final pathology
- Participant requests to be withdrawn from study
- Completion of 10-year assessment
- Lost to follow-up
- Investigator discretion
- Screen failure
- Death

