7 STATISTICAL CONSIDERATIONS

The primary goal of this study is to determine if there is a difference in biochemical cure rates based on postoperative stimulated thyroglobulin levels (stim-Tg) at 3 months, primarily focusing on the rates of athyroglobulinemia, in patients with clinically node negative PTC undergoing TT and with and without pCND. Serum Tg, especially when TSH-stimulated, is a very sensitive and specific marker for residual thyroid tissue, persistent or recurrent differentiated thyroid cancer of follicular cell origin, in the absence of anti-Tg antibodies. Because patients with differentiated thyroid cancer whose Tg and/or stim-Tg becomes undetectable after treatment(s) are typically considered free of disease in the absence of radiographic evidence of tumor, we use athyroglobulinemia as a surrogate for biochemical remission. We conservatively estimate that there should be at least a 20% higher rate of athyroglobulinemia in patients undergoing TT and pCND ($\theta_2 = 0.4$) compared to TT alone ($\theta_1 = 0.2$) during early postoperative period. With a total of 180 evaluable participants (approximately n=90 for each arm) who have no anti-thyroglobulin

Abbreviated Title: Prophylactic Central Neck Dissection

Version Date: 01/15/2019

antibody, the trial will have 80% power ($\beta=0.20$) to detect the difference between 0.2 and 0.4 using a Fisher's exact test with two-sided significance level (α) of 0.05.

The protocol will not have any stratification at the time of randomization because there are no known factors associated with athyroglobulinemia. Because this study only enrolls patients with low-risk PTC, it is unlikely that there would be many patients with advanced age and advanced PTC that may be unevenly distributed which may confound with the results of the study.

This study will be monitored by the NCI/CCR Data Safety and Monitoring Board, both for toxicity as well as efficacy and futility with respect to the primary endpoint.

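### At the interim look an efficacy crossing stops the trial while futility stops only accrual, and the documents do not say what then happens to patients already randomised

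*Combined protocol and SAP*

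**What the plan says.** Section 7 plans one interim look, once 90 patients without anti-thyroglobulin antibody have been evaluated, at the first DSMB meeting after that point. Two rules apply.

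- **Efficacy.** If the two-tailed p-value comparing the athyroglobulinemia rates is below 0.0054, "then the trial will be stopped at that time and a significant difference declared".
- **Futility.** If the rate with pCND is the same as or lower than with TT alone, "then accrual will stop because of very small probability of achieving a statistically significant difference" in favour of pCND.

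Section 7 does not define stopping the trial and does not mention patients already randomised. Section 6.4.2 speaks of early termination only when it says when investigators may see results.

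Follow-up is set elsewhere. Section 3.3.2 states: "Surveillance for persistent or recurrence disease will be performed every year for 10 years". It also schedules SF-36 at 5 and 10 years and holds the blind until after the 10-year visit unless medical need requires otherwise. The off-study reasons in Section 3.3.3 apply to the individual patient. They include "Completion of 10-year assessment" and investigator discretion, but not early stopping of the trial.

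**The concern.** The decision at the look rests on a 3-month marker that Section 7 itself calls a surrogate for biochemical remission. Whether an early gain lasts is an open question in the protocol's own background. Section 1.2.2.2 cites retrospective work in which stim-Tg before ablation was lower with pCND, "but no difference was observed at 6 months post remnant ablation". Section 1.2.3 puts about half of recurrences in the first 5 years and 75% within 10. Recurrence and long-term quality of life are listed secondary objectives in Section 1.1.2.

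A rule that stops the trial on the early marker, without saying that follow-up continues, leaves those objectives to be settled after the result is known. Two further matters are open at the same point: what happens to patients randomised but not yet tested, and how a difference selected for having crossed a boundary is to be estimated.

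**Working it through.** **1. The plan's own power.** Inputs from Section 7: rates 0.2 and 0.4, 90 evaluable per arm, Fisher's "exact test with two-sided significance level" of 0.05. With x and y the numbers with athyroglobulinemia on TT alone and on TT + pCND, power is the sum over all (x, y) of b(x; 90, 0.2) × b(y; 90, 0.4) where the Fisher p is at most 0.05. Result: 80.2%, against 80% stated. The figure reproduces.

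**2. Chance of crossing.** The same sum with 45 per arm (90 split 1:1) and p < 0.0054 gives 18.0%. Virtually all of it favours pCND, although the boundary is two-tailed. Section 7 does not name the interim test; a pooled z-test gives 24.1%. Under an assumed 0.2 v 0.5 the chance is 52% (Fisher) to 61% (pooled z).

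**3. Overstatement.** The mean of (y − x)/45 among crossings that favour pCND is 33.6 points. The true difference is 40 − 20 = 20 points, so the average excess is 13.6 points.

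**4. Smallest difference that crosses (Fisher).** It depends on the TT-alone count:

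| TT alone | TT + pCND | Difference | p |
|---|---|---|---|
| 0/45 | 9/45 | 20.0 points | 0.0025 |
| 4/45 | 16/45 | 26.7 points | 0.0045 |
| 5/45 | 18/45 | 28.9 points | 0.0032 |
| 9/45 | 23/45 | 31.1 points | 0.0039 |

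For TT-alone counts of 5 to 12 the threshold is 28.9 to 31.1 points.

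**5. Follow-up in hand at the look.** Allowing for 20% antibody-positive patients (Section 7), 90 evaluable means 90/0.8 = 112.5 enrolled. Let T be the years needed to enrol them.

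- 225 patients over 6 to 7 years is 37.5 to 32.1 per year, so T is 3.0 to 3.5.
- At the current 25 to 30 cases per year, T is 4.5 to 3.75.

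Assume even accrual and a look 3 months after the last of these patients. The share past 1 year is (T + 0.25 − 1)/T: 2.25/3.0 = 75% at T = 3.0, and 3.75/4.5 = 83% at T = 4.5. The earliest patient has at most 4.5 + 0.25 = 4.75 years, so none has reached year 5. If the meeting comes a year later, the earliest patient has 4.25 to 5.75 years; a few could have reached year 5 at the slowest rate, and none year 10.

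**6. Patients awaiting the 3-month test.** At an assumed 25 to 37.5 per year:

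- prompt look: 25 × 0.25 = 6 to 37.5 × 0.25 = 9
- meeting a year later: 25 × 1.25 = 31 to 37.5 × 1.25 = 47 randomised beyond the interim set; most of these would have been tested by then, but the rule, tied to 90 evaluated patients, does not say whether they count.

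**7. The sections side by side.** Section 7 stops the trial at that time. Section 3.3.2 runs surveillance and the blind to year 10. Section 3.3.3 gives no off-study reason that an efficacy stop would trigger. No sentence says that follow-up ends on a crossing, none says that it continues, and no order of precedence is given.

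**The case against.** A reader might infer that crossing the boundary would end the 1-year, quality-of-life and 10-year follow-up for all of the roughly 112 patients then enrolled. The documents do not say so. That reading rests on the word trial in one clause, and Sections 3.3.2 and 3.3.3 point the other way. It is reasonable to read the clause as stopping enrolment and the primary comparison, with scheduled visits going on. The consequence would also be too broad: with a prompt look, most interim patients would already be past 1 year, and so past the point at which the cited early difference had faded. These objections stand, and they limit the point to an unresolved conflict with long-term exposure.

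A reader might also infer that crossing always needs a difference of 29 to 31 points. It does not; 20 points is enough when the TT-alone count is zero.

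It can fairly be said that overstatement after an early stop is common to group-sequential designs, and that neither 18.0% nor 33.6 points shows that follow-up ends. That is true. Those figures show how likely the clause is to be used and what would be reported if it were. They do not decide which section governs.

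The objection does not remove the difference in wording between two rules at the same meeting, or the silence about randomised patients. Investigator discretion in Section 3.3.3 would permit either course after the result is known.

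**Conclusion.** The point holds as a conflict within a pre-specified decision rule, not as a stated plan to abandon follow-up. If the literal wording were applied, the loss would fall mainly on the 5- and 10-year quality-of-life data and later recurrence data, plus 1-year data for the most recently enrolled 17-25% of interim patients (100 − 83 to 100 − 75). Patients still awaiting the 3-month test, about 6-9 with a prompt look, would have no stated place in the result, and neither would the 31-47 randomised beyond the interim set if the meeting came a year later.

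Under the planned rates the clause would be used in 18.0% of trials, with an average overstatement of 13.6 points and no adjusted estimate planned. These figures assume 45 per arm, Fisher's test at the look, even accrual at 25-37.5 per year and 20% antibody-positive patients. The pooled z-test raises the crossing chance to 24.1%. The wording should be settled before the interim look, because a choice made afterwards could be influenced by the result.

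**What to change.** Reconcile Section 7 with Sections 3.3.2 and 3.3.3 by replacing the efficacy clause with wording that states the following:

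1. An efficacy crossing stops accrual.
2. All randomised patients complete the scheduled 3-month stim-Tg and the blinded follow-up already planned to year 10.
3. Patients randomised before the stop are included in an updated analysis of the primary endpoint, reported alongside the interim result.
4. The difference is reported with a point estimate and confidence interval adjusted for the interim look, for example median-unbiased.

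The same edit should name the interim test, since Section 7 does not.

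The cost is one or two sentences and a little more analysis. No visit is added, because the follow-up is already in the study calendar. The adjusted estimate will be somewhat smaller than the raw interim difference, which is a price worth paying.
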